10.5.1. Special Safety Topics

10.5.1.1. Hypoglycemia

Upon ICF signing, all participants will be educated about signs and symptoms of hypoglycemia, how to treat hypoglycemia, and how to collect appropriate information for each episode of hypoglycemia.

Hypoglycemia may be identified by spontaneous reporting of symptoms from participants (whether confirmed or unconfirmed by simultaneous glucose values) or by BG samples collected during study visits.

All participants with T2DM and who develop diabetes during the study will be provided with glucometers.

Participants with T2DM will be provided a diary to record relevant information (for example, glucose values, symptoms).

All hypoglycemic episodes are to be recorded on a specific eCRF and should not be otherwise recorded as AEs unless the event meets severe criteria. If a hypoglycemic event meets severe criteria (see definition below), it should be recorded as serious on the AE eCRFs, and reported to the sponsor as an SAE. To avoid duplicate reporting, all consecutive BG values <70 mg/dL (<3.9 mmol/L) occurring within a 1-hour period may be considered to be a single hypoglycemic event (Weinberg et al. 2010; Danne et al. 2013).

Investigators should use the following definitions and criteria when diagnosing and categorizing an episode considered to be related to hypoglycemia (the BG values in this section refer to values determined by a laboratory or International Federation of Clinical Chemistry and Laboratory Medicine blood-equivalent glucose meters and strips) in accordance with the 2020 American Diabetes Association position statement on glycemic targets (ADA 2020):

Glucose Alert Value (Level 1):

- Documented symptomatic hypoglycemia is defined as any time a participant feels that he or she is experiencing symptoms and/or signs associated with hypoglycemia and has a BG level of <70 mg/dL (<3.9 mmol/L).
- Documented asymptomatic hypoglycemia is defined as any event not accompanied by typical symptoms of hypoglycemia, but with a measured BG <70 mg/dL (<3.9 mmol/L).
- Documented unspecified hypoglycemia is defined as any event with no information about symptoms of hypoglycemia available, but with a measured BG <70 mg/dL (<3.9 mmol/L).

Clinically Significant Hypoglycemia (Level 2):

• Documented symptomatic hypoglycemia is defined as any time a participant feels that he or she is experiencing symptoms and/or signs associated with hypoglycemia and has a BG level of <54 mg/dL (<3.0 mmol/L).

• Documented asymptomatic hypoglycemia is defined as any event not accompanied by typical symptoms of hypoglycemia but with a measured BG <54 mg/dL (<3.0 mmol/L).

• Documented unspecified hypoglycemia is defined as any event with no information about symptoms of hypoglycemia available but with a measured BG <54 mg/dL (<3.0 mmol/L).

Severe Hypoglycemia (Level 3):

• Severe hypoglycemia is defined as an episode with severe cognitive impairment requiring the assistance of another person to actively administer carbohydrate, glucagon, or other resuscitative actions. These episodes may be associated with sufficient neuroglycopenia to induce seizure or coma. Blood glucose measurements may not be available during such an event, but neurological recovery attributable to the restoration of BG to normal is considered sufficient evidence that the event was induced by a low BG concentration.

Nocturnal Hypoglycemia:

Nocturnal hypoglycemia is a hypoglycemia event (including severe hypoglycemia) that occurs at night, presumably during sleep.

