8.3.1. Timing and Mechanism for Collecting Events

This table describes the timing, deadlines, and mechanism for collecting events.

Event	Collection Start	Collection Stop	Timing for Reporting to Sponsor or Designee	Mechanism for Reporting	Back-up Method of Reporting
Adverse Ever	nt				
AE	Signing of the informed consent form (ICF)	Participation in study has ended	As soon as possible upon site awareness	AE eCRF	N/A
Serious Adve	erse Event				
SAE and SAE updates – prior to start of study drug and deemed reasonably possibly related with study procedures	Signing of the informed consent form (ICF)	Start of study drug	Within 24 hours of awareness	SAE eCRF	SAE paper form

Event	Collection Start	Collection Stop	Timing for Reporting to Sponsor or Designee	Mechanism for Reporting	Back-up Method of Reporting
SAE* and SAE updates – after start of study drug	Start of study drug	Participation in study has ended	Within 24 hours of awareness	SAE eCRF	SAE paper form
SAE* – after participant's study participation has ended and the investigator becomes aware	After participant's study participation has ended	N/A	Promptly	SAE paper form	N/A
Pregnancy					
Pregnancy in female participants and female partners of male participants	After the start of study drug	Four months after the last injection for female partners of male participants and 2 months after the last injection for female participants	Within 24 hours of learning of the pregnancy	Pregnancy paper form eCRF	Pregnancy paper form
Product Com	plaints				
PC associated with an SAE or might have led to an SAE	Start of study drug	End of study drug	Within 24 hours of awareness	Product Complaint form	N/A
PC not associated with an SAE	Start of study drug	End of study drug	Within 1 business day of awareness	Product Complaint form	N/A

Event	Collection Start	Collection Stop	Timing for Reporting to Sponsor or Designee	Mechanism for Reporting	Back-up Method of Reporting
Updated PC information	_	_	As soon as possible upon site awareness	Originally completed Product Complaint form with all changes signed and dated by the investigator	N/A
PC (if investigator becomes aware)	Participation in study has ended	N/A	Promptly	Product Complaint form	N/A

Abbreviations: eCRF = electronic case report form; N/A = not applicable; PC = product complaint; SAE = serious adverse event.

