10.3.2. Definition of SAE

If an event is not an AE per the definition above, then it cannot be an SAE even if serious conditions are met (for example, hospitalization for signs/symptoms of the disease under study, death due to progression of disease).

SAE is defined as any untoward medical occurrence that, at any dose:

a. Results in death

b. Is life-threatening

The term "life-threatening" in the definition of "serious" refers to an event in which the participant was at risk of death at the time of the event. It does not refer to an event, which hypothetically might have caused death, if it were more severe.

c. Requires inpatient hospitalization or prolongation of existing hospitalization

- In general, hospitalization signifies that the participant has been admitted to the hospital for observation and/or treatment that would not have been appropriate in the physician's office or outpatient setting. Complications that occur during hospitalization are AEs. If a complication prolongs hospitalization or fulfills any other serious criteria, the event is serious. When in doubt as to whether "hospitalization" occurred or was necessary, the AE should be considered serious.
- Hospitalization for elective treatment of a preexisting condition that did not worsen from baseline is not considered an AE.

d. Results in persistent disability/incapacity

• The term disability means a substantial disruption of a person's ability to conduct normal life functions.

• This definition is not intended to include experiences of relatively minor medical significance such as uncomplicated headache, nausea, vomiting, diarrhea, influenza, and accidental trauma (for example, sprained ankle) which may interfere with or prevent everyday life functions but do not constitute a substantial disruption.

e. Is a congenital anomaly/birth defect

• Abnormal pregnancy outcomes (for example, spontaneous abortion, fetal death, stillbirth, congenital anomalies, ectopic pregnancy) are considered SAEs.

f. Other situations:

- Medical or scientific judgment should be exercised in deciding whether SAE reporting
 is appropriate in other situations such as important medical events that may not be
 immediately life-threatening or result in death or hospitalization but may jeopardize the
 participant or may require medical or surgical intervention to prevent one of the other
 outcomes listed in the above definition. These events should usually be considered
 serious.

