- Severe: A type of adverse event that interrupts usual activities of daily living, or significantly affects clinical status, or may require intensive therapeutic intervention. An AE that is assessed as severe should not be confused with an SAE. Severe is a category utilized for rating the intensity of an event; and both AEs and SAEs can be assessed as severe.

An event is defined as 'serious' when it meets at least 1 of the predefined outcomes as described in the definition of an SAE, NOT when it is rated as severe.

Assessment of Causality

- The investigator is obligated to assess the relationship between study drug and each occurrence of each AE/SAE.
- A "reasonable possibility" of a relationship conveys that there are facts, evidence, and/or arguments to suggest a causal relationship, rather than a relationship cannot be ruled out.
- The investigator will use clinical judgment to determine the relationship.
- Alternative causes, such as underlying disease(s), concomitant therapy, and other risk factors, as well as the temporal relationship of the event to study drug administration will be considered and investigated.
- The investigator will also consult the IB in his/her assessment.
- For each AE/SAE, the investigator **must** document in the medical notes that he/she has reviewed the AE/SAE and has provided an assessment of causality.
- There may be situations in which an SAE has occurred, and the investigator has minimal information to include in the initial report to sponsor or designee. However, it is very important that the investigator always make an assessment of causality for every event before the initial transmission of the SAE data to sponsor or designee.
- The investigator may change his/her opinion of causality in light of follow-up information and send an SAE follow-up report with the updated causality assessment.
- The causality assessment is one of the criteria used when determining regulatory reporting requirements.

Follow-up of AEs and SAEs

• The investigator is obligated to perform or arrange for the conduct of supplemental measurements and/or evaluations as medically indicated or as requested by sponsor or designee to elucidate the nature and/or causality of the AE or SAE as fully as possible. This may include additional laboratory tests or investigations, histopathological examinations, or consultation with other health care professionals.

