3.14.3.7. Hypoglycemia

The following categories in accordance with the 2021 American Diabetes Association position statement on glycemic targets (ADA 2021) will be defined in the database.

Glucose Alert Value (Level 1):

- **Documented symptomatic hypoglycemia** is defined as any time a participant feels he/she is experiencing symptoms and/or signs associated with hypoglycemia, and has a blood glucose (BG) level of <70 mg/dL (<3.9 mmol/L) and ≥54 mg/dL (≥3.0 mmol/L).
- **Documented asymptomatic hypoglycemia** is defined as any event not accompanied by typical symptoms of hypoglycemia, but with a measured BG <70 mg/dL (<3.9 mmol/L) and $\ge54 \text{ mg/dL}$ ($\ge3.0 \text{ mmol/L}$).
- **Documented unspecified hypoglycemia** is defined as any event with no information about symptoms of hypoglycemia available, but with a measured BG <70 mg/dL (<3.9 mmol/L) and ≥54 mg/dL (≥3.0 mmol/L).

Documented Clinically Significant Hypoglycemia (Level 2):

- **Documented symptomatic hypoglycemia** is defined as any time a participant feels he/she is experiencing symptoms and/or signs associated with hypoglycemia and has a BG level of <54 mg/dL (<3.0 mmol/L).
- **Documented asymptomatic hypoglycemia** is defined as any event not accompanied by typical symptoms of hypoglycemia but with a measured BG <54 mg/dL (<3.0 mmol/L).
- **Documented unspecified hypoglycemia** is defined as any event with no information about symptoms of hypoglycemia available but with a measured BG <54 mg/dL (<3.0 mmol/L).

Severe Hypoglycemia (Level 3):

Severe hypoglycemia is defined as an episode with severe cognitive impairment requiring the assistance of another person to actively administer carbohydrate, glucagon, or other resuscitative actions. These episodes may be associated with sufficient neuroglycopenia to induce seizure or coma. Plasma glucose (PG) measurements may not be available during such an event, but neurological recovery attributable to the restoration of PG to normal is considered sufficient evidence that the event was induced by a low PG concentration.

Other hypoglycemia categories:

Nocturnal hypoglycemia is defined as any hypoglycemic event that occurs between bedtime and waking. If a hypoglycemic event meets the criteria of severe, the event would specifically be collected as an SAE. Serious hypoglycemia is defined by pharmacovigilance criteria and will also be captured with an SAE form.

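### The hypoglycemia section bars adverse event recording unless an episode is severe, which conflicts with the general SAE rules and the SAP for episodes that are serious but not severe

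*Protocol*

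**What the plan says.** Protocol 10.5.1.1 has all hypoglycemic episodes entered on a specific eCRF and adds that they "should not be otherwise recorded as AEs unless the event meets severe criteria". For an episode that is severe, "it should be recorded as serious on the AE eCRFs, and reported to the sponsor as an SAE". The section points to its own definition: "Severe hypoglycemia is defined as an episode with severe cognitive impairment requiring the assistance of another person", that is, Level 3. It gives no other route from a hypoglycemic episode to the AE or SAE forms.

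The general rules use a different test. Protocol 10.3.2 lists outcomes that make an event serious, one being "Requires inpatient hospitalization or prolongation of existing hospitalization". Protocol 10.3.4 gives the test for calling an event serious: "meets at least 1 of the predefined outcomes as described in the definition of an SAE, NOT when it is rated as severe". Protocol 8.3.1 has a row for "SAE* and SAE updates – after start of study drug", with reporting on the SAE eCRF within 24 hours of awareness.

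SAP 3.14.3.7 names two groups. On severe episodes it agrees with the protocol: "If a hypoglycemic event meets the criteria of severe, the event would specifically be collected as an SAE". It then adds: "Serious hypoglycemia is defined by pharmacovigilance criteria and will also be captured with an SAE form".

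**The concern.** Severe and serious are separate tests, and 10.5.1.1 opens the AE form only to the first. A participant admitted with hypoglycemia who was never severely cognitively impaired meets the seriousness test and not the Level 3 test. For that participant the section headed Hypoglycemia tells the site not to make an AE entry, while the general safety sections tell it to report an SAE within 24 hours. Site staff handling an episode are likely to turn to the hypoglycemia section.

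At stake is the capture of a recognised risk. Protocol 6.5 recommends reducing sulfonylurea or insulin at the start of study drug in order to lower the risk of hypoglycemia. An episode left off the SAE forms would be absent from expedited reporting, from the SAE summary and listing in SAP 3.14.1.4, and from the narratives that SAP 3.14.2 triggers on serious events.

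**Working it through.** The documents state no figure on this point and no formula applies. The check sets the recording rules side by side.

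1. **Is severe narrower than serious?** Yes. The Level 3 definition in 10.5.1.1 rests on cognitive impairment and help from another person; hospitalization is not part of it. The list in 10.3.2 includes death, threat to life, hospitalization and important medical events. The warning in 10.3.4 concerns the intensity rating rather than Level 3, but it confirms that seriousness turns on outcome.

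2. **Would such an episode be an AE at all?** Yes. Section 10.3.2 requires an SAE first to be an AE by definition. Section 10.3.1 defines an AE as any untoward medical occurrence, and its carve-out for the disease under study concerns heart failure, not hypoglycemia.

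3. **Is hypoglycemia exempt from SAE reporting?** No exemption is written. The protocol does spell one out for endpoint and disease-progression events (8.3.2 and the footnote to the table in 8.3.1). That one covers deaths and heart failure events.

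4. **Do neighbouring sections handle this differently?** Yes. Section 10.5.1.6 (arrhythmias) sends events meeting the 10.3.2 criteria to SAE reporting. Section 10.5.1.7 (hypersensitivity) does the same for any serious criterion. Section 10.5.1.2 leaves the seriousness of unconfirmed pancreatitis to the investigator. Only the hypoglycemia section pairs an instruction not to record with no seriousness clause, which suggests an omission.

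5. **Where does each kind of episode end up?**

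| Episode | 10.5.1.1 read literally | 8.3.1 with 10.3.2 | SAP hypoglycemia outputs (3.14.3.7) |
|---|---|---|---|
| Level 3 | AE eCRF as serious, and SAE | SAE | Incidence, rate and listing |
| Level 2, admitted, not severe | Hypoglycemia eCRF only | SAE | Incidence, rate and listing |
| Level 1, admitted, not severe | Hypoglycemia eCRF only | SAE | Not in the Level 2/3 outputs |
| No glucose value, admitted, not severe | Hypoglycemia eCRF only | SAE | Not in the Level 2/3 outputs |

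The last row is a real category: 10.5.1.1 accepts episodes identified by symptoms without a confirming glucose value, whereas Levels 1 and 2 both require a measured value. The SAP also censors hypoglycemia data when a new antihyperglycemic medication is received, so a Level 2 episode after that point can drop out of its last column too.

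6. **How many episodes?** Protocol 2.2 discusses 40% to 50% of participants having T2DM, conditionally. With 700 participants that is 0.40 × 700 = 280 to 0.50 × 700 = 350. The documents give no rate of episodes that are serious but not severe, so no event count follows from this base.

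**The case against.** The strongest reply is that the general duty is untouched. Sections 8.3.1 and 10.3.2 already require a hospitalized episode to be reported as an SAE. Section 10.3.2 even says that doubt about hospitalization is to be resolved towards seriousness. The sentence in 10.5.1.1 can be read as form routing, meant to keep ordinary low glucose values off the AE form, and not as a change to what counts as serious. On that reading SAP 3.14.3.7 simply restates the general duty. In addition, the eCRF completion instructions and site training are not part of these documents and may already carry a seriousness prompt. The recording rule is also the same in both blinded arms.

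Much of this stands. A reader might infer that serious, non-severe episodes can never reach the SAE data, that all of them are lost to expedited reporting, or that the SAP says the reverse of the protocol. The documents support none of these. The general rules still apply, every episode is on the hypoglycemia eCRF, and the SAP agrees with the protocol on severe episodes and with 8.3.1 on serious ones.

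The reply does not remove the conflict. Section 10.5.1.1 contains an explicit instruction not to record, with a single stated exception that is narrower than seriousness. A site can follow that section to the letter and still miss a 24-hour report. The hypoglycemia eCRF does not itself trigger SAE reporting, the SAE tables or the narratives.

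**Conclusion.** The point holds as an internal inconsistency, and 10.5.1.1 is wrong as written. Its recording rule conflicts with Protocol 8.3.1 and 10.3.2, departs from the distinction drawn in 10.3.4, and does not provide for the serious episodes that SAP 3.14.3.7 expects on an SAE form.

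The consequence is a risk of under-reporting, not a demonstrated loss. It arises only where a site lets the specific rule override the general one. The most exposed cases are serious Level 1 episodes and episodes without a glucose value, because the Level 2/3 listing would not show them either. The number affected cannot be estimated and may be zero; any count would need an assumed rate with no basis in the documents. No primary or key secondary analysis is affected. The correction is still worth making, because sites should not have to choose between two written rules for an expedited safety report.

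**What to change.** Reconcile the passages on recording. In Protocol 10.5.1.1, extend the exception after the reference to severe criteria with: *or any seriousness criterion in Section 10.3.2; any such event is recorded as serious on the AE eCRF and reported as an SAE*. This brings the section into line with 10.5.1.6, 10.5.1.7 and SAP 3.14.3.7. It changes recording only and leaves clinical management alone.

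Before database lock, query every hypoglycemia eCRF episode that overlaps a hospitalization or another seriousness criterion, and enter any SAE that was missed. The query should cover all levels and episodes without a glucose value. Restricting it to Level 2 would pass over the cases that the SAP listing also omits.

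The cost is one protocol sentence or a site letter, one data query, and possibly a few extra SAE reports.

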10.5.1.2. Pancreatitis

Acute pancreatitis is defined as an AE of interest in all trials with tirzepatide, including this trial.

Acute pancreatitis is an acute inflammatory process of the pancreas that may also involve peripancreatic tissues and/or remote organ systems (Banks and Freeman 2006). The diagnosis of acute pancreatitis requires 2 of the following 3 features:

- abdominal pain, characteristic of acute pancreatitis (generally located in the epigastrium and radiates to the back in approximately half the cases) (Banks and Freeman 2006; Koizumi et al. 2006); the pain is often associated with nausea and vomiting
- serum amylase (total and/or pancreatic) and/or lipase ≥3X ULN, and
- characteristic findings of acute pancreatitis on CT scan or MRI.

If acute pancreatitis is suspected, appropriate laboratory tests (including levels of pancreatic amylase and lipase) should be obtained via the central laboratory (and locally, if needed).

Imaging studies, such as abdominal CT scan with or without contrast, MRI, or gallbladder ultrasound, should be performed. Abdominal ultrasound may be used as an alternative method only if CT and MRI cannot be performed. If laboratory values and/or abdominal imaging support the diagnosis of acute pancreatitis, the participant must discontinue therapy with tirzepatide but will continue in the study. A review of the participant's concomitant medications should be conducted to assess any potential causal relationship with pancreatitis.

Each AE of pancreatitis must be reported. If typical signs and/or symptoms of pancreatitis are present and confirmed by laboratory values (lipase or amylase [total and/or pancreatic]) and imaging studies, the event must be reported as an SAE. For a potential case that does not meet all of these criteria, it is up to the investigator to determine the seriousness of the case (AE or SAE) and the relatedness of the event to study drug(s).

Each participant will have measurements of p-amylase and lipase (assessed at the central laboratory) as shown on the SoA (Section 1.3) to assess the effects of the investigational doses of tirzepatide on pancreatic enzyme levels. Serial measurements of pancreatic enzymes have limited clinical value for predicting episodes of acute pancreatitis in asymptomatic participants (Nauck et al. 2017; Steinberg et al. 2017a, 2017b). Thus, further diagnostic follow-up of cases of asymptomatic pancreatic hyperenzymemia (lipase and/or pancreatic amylase ≥3X ULN) is not mandated but may be performed based on the investigator's clinical judgment and assessment of the participant's overall clinical condition. Only cases of pancreatic hyperenzymemia that undergo additional diagnostic follow-up and/or are accompanied by symptoms suggestive of pancreatitis will be submitted for adjudication.

All suspected cases of acute or chronic pancreatitis will be adjudicated by an independent clinical endpoint committee. In addition, AEs of severe or serious abdominal pain of unknown etiology will also be submitted to the adjudication committee to assess for possible pancreatitis or other pancreatic disease. Relevant data from participants with acute or chronic pancreatitis and those with severe or serious abdominal pain will be entered into a specifically designed eCRF page. The adjudication committee representative will enter the results of adjudication in a corresponding eCRF page.

